## **12. CONFIDENTIALITY/PUBLICATION OF THE STUDY**

The existence of this Study is confidential and should not be discussed with persons outside of the Study. Results will be submitted for publication and presentation at national and/or international meetings. A manuscript will be submitted to peer-review journals for publication but there is no guarantee of acceptance.

All study data will be collected on appropriate Case Report Forms (CRFs). No protected health information will be included on the forms. CRFs will be retained in the patient's file for a minimum period of 3 years. Collected information will only be used for purposes of this study and no information will be sold to third parties. The following people will have access to your study records:

- Study Doctor and staff involved with the study
- Study Monitor or Auditor
- Sponsor Company or Research Institution
- Review boards or accrediting agencies

- Other State or Federal Regulatory Agencies

The de-identified data may be shared with other researchers for future analysis.

## **13. QUALITY COMPLAINTS AND ADVERSE EVENTS**

All subjects will be monitored for adverse events over the course of the study. A place to record any adverse event is included on each case report form.

### ***13.1. General Information***

An Adverse Event (AE) is any untoward medical occurrence in a subject who is administered a study treatment regardless of whether or not the event has a causal relationship with the treatment. An AE, therefore, can be any unfavorable or unintended sign (including an abnormal laboratory finding), symptom, or disease temporally associated with the study treatment, whether or not related to the treatment. In clinical studies, an AE can include an untoward medical occurrence occurring at any time, including run-in or washout periods, even if no study treatment has been administered.

### ***13.2. Monitoring for Adverse Events***

At each visit, after the subject has had the opportunity to spontaneously mention any problems, the Investigator should inquire about AEs by asking if the patient has any problems.

### ***13.3. Procedures for Recording and Reporting AEs and SAEs***

Subsequent to signing an informed consent form, all untoward medical occurrences that occur during the course of the study must be documented on an Adverse Event Form (AEF). A separate AEF must be filled out for each event. When possible, signs and symptoms indicating a common underlying pathology should be documented as one comprehensive event. For each recorded event, the AE documentation must include the onset date, outcome, resolution date (if event is resolved), intensity (ie, severity), any action with study treatment taken as a result of the event, and an assessment of the adverse event's relationship to the study treatment.

#### **Nonserious Adverse Events**

A nonserious AE is defined as any untoward change in a subject's medical health that does not meet serious criteria noted below (eg, is not life-threatening, does not require hospitalization, does not prolong a current hospitalization, is not disabling, etc.). All adverse events must be reported regardless of whether or not they are related to the study treatment.

For nonserious adverse events, an AEF containing all available information will be collected on a routine basis and submitted to the Medical Monitor at the close of the study.

#### **Serious Adverse Events**

A serious adverse event (SAE) is defined as any adverse experience that meets any of the following criteria:

- Results in death.
- Is life-threatening.

NOTE: Life-threatening means that the subject was at immediate risk of death from the reaction as it occurred, ie, it does not include a reaction which hypothetically might have caused death had it occurred in a more severe form.

- Requires inpatient hospitalization or prolongation of existing hospitalization.

NOTE: In general, hospitalization signifies that the individual remained at the hospital or emergency ward for observation and/or treatment (usually involving an overnight stay) that would not have been appropriate in the physician's office or an out-patient setting. Complications that occur during hospitalization are AEs. If a complication prolongs hospitalization or fulfills any other serious criteria, the event is serious. When in doubt as to whether "hospitalization" occurred, the event should be considered serious.

- Results in persistent or significant disability/incapacity. Disability is defined as a substantial disruption of a person's ability to conduct normal life functions.

NOTE: The term disability means a substantial disruption of a person's ability to conduct normal life functions. This definition is not intended to include experiences of relatively minor medical significance such as uncomplicated headache, nausea, vomiting, diarrhea, influenza, or accidental trauma (eg, sprained ankle) which may interfere or prevent everyday life functions but do not constitute a substantial disruption.

- Is an important medical event. An important medical event is an event that may not result in death, be life-threatening, or require hospitalization but may be considered an SAE when, based upon appropriate medical judgment, it may jeopardize the subject and may require medical or surgical intervention to prevent one of the outcomes listed in the definitions for SAEs. Examples of such medical events include allergic bronchospasm requiring intensive treatment in an emergency room or at home, blood dyscrasias or convulsions that do not result in subject hospitalization, or the development of drug dependency or drug abuse.

All available information on a serious adverse event(s) and any other associated AE, if applicable, must be forwarded to the study coordinator for forwarding to the Medical Monitor immediately (ie, within one working day of the Investigator's or site's knowledge of the event) as follows:

- In studies utilizing EDC (electronic data capture), all available information for the SAE and any associated AE(s) must be entered immediately into the EDC system.
- Additional information for any applicable event is to be reported as soon as it becomes available.

In addition to the reporting of serious adverse events to the study Medical Monitor, the SAE must be reported to the IRB / IEC according to their requirements.

The investigator must document all adverse device events (serious and nonserious but related) and all serious adverse events (related and unrelated) on the Adverse Device

Effect and Serious Adverse Event Form. Any device quality complaints will also be documented.

- **Both the Quality Complaint Form and the Adverse Device Effect and Serious Adverse Event Form must be faxed immediately to the study coordinator at [name] or emailed to [contact].**
- **Additional relevant information is to be reported as soon as it becomes available.**

#### 12.3.1 Intensity and Causality Assessments

For every adverse event and quality complaint, the investigator must assess the causality as Related or Not Related to the medical device under investigation. An assessment of causality will also be performed by the Medical Monitor utilizing the same definitions, as shown below:

##### ***Causality***

Related	An adverse event or quality complaint classified as related may be either definitely related or possibly related where a direct cause and effect relationship with the medical device has not been demonstrated, but there is a reasonable possibility that the adverse event or quality complaint was caused by the medical device.
Not Related	An adverse event or quality complaint classified as not related may either be definitely unrelated or simply unlikely to be related (i.e., there are other more likely causes for the adverse event or quality complaint).

Where appropriate, the investigator must assess the intensity (severity) of the adverse event as mild, moderate, or severe based on medical judgment with consideration of any subjective symptom(s), as defined below:

***Intensity (Severity)***

Mild	An adverse event is mild if the subject is aware of but can easily tolerate the sign or symptom.
Moderate	An adverse event is moderate if the sign or symptom results in discomfort significant enough to cause interference with the subject's usual activities.
Severe	An adverse event is severe if the sign or symptom is incapacitating and results in the subject's inability to work or engage in their usual activities.

The investigator must document any action taken (i.e., medication, intervention, or treatment plan) and outcome of the adverse event or quality complaint when applicable.

***13.4. Follow-Up of Adverse Events and Quality Complaints***

The investigator is responsible for adequate and safe medical care of subjects during the study and for ensuring that appropriate medical care and relevant follow-up procedures are maintained after the study. Any additional data from these follow-up procedures must be documented and available to the study coordinator who, with the Medical Monitor, will determine when the data need to be documented on the CRFs.

***13.5. Safety Analyses***

The type, severity, duration and frequency of reported ocular adverse events will be tabulated. Adverse events will also be summarized for events that were considered treatment-related.

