## **10. ANALYSIS PLAN**

### ***10.1. Analysis Data Sets***

All subjects who are enrolled in the study will be evaluated for safety. Efficacy analyses will be performed based on data from those eyes where uncomplicated Verion-LenSx guided arcuate incisions were completed.

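### Section 13.5 plans no table or listing for non-ocular adverse events judged not related, including serious ones, although the protocol collects them all

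*Combined protocol and SAP*

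**What the plan says.** Collection is broad. Section 13.1 does not limit an adverse event to the eye; it includes any unfavourable sign, "symptom, or disease temporally associated with the study treatment, whether or not related to the treatment". Section 13.3 requires that, once consent is signed, "all untoward medical occurrences that occur during the course of the study must be documented on an Adverse Event Form (AEF". Under Nonserious Adverse Events the rule is repeated: "All adverse events must be reported regardless of whether or not they are related to the study treatment". Under Serious Adverse Events the investigator must document "all serious adverse events (related and unrelated", with notification to the Medical Monitor within one working day, and "the SAE must be reported to the IRB / IEC according to their requirements".

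The population is also broad. Section 10.1 states: "All subjects who are enrolled in the study will be evaluated for safety".

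The analysis is narrower. Section 13.5 names two outputs. One is a tabulation: "The type, severity, duration and frequency of reported ocular adverse events will be tabulated". The other is a summary: "Adverse events will also be summarized for events that were considered treatment-related". Sections 10.2 and 10.3 give only general descriptive methods, the software and the significance level. They name no adverse event output.

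**The concern.** The first output is limited by site and the second by causality. An event outside both limits has no place in the planned results, even though the site must record it. The events that matter most here are serious ones. A hospitalization or death from a non-ocular cause during follow-up, judged not related, could be left out of the safety results by an analyst who follows section 13.5 exactly.

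This is a stated restriction, not detail left for later, because the tabulation sentence says which events it covers. Section 12 says the results will be submitted for publication. A reader of that report would see an ocular table and a related-event summary and could not tell whether any other serious event had occurred.

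**Working it through.** No plan figure needs reproducing, and no sample size, power or margin enters. The check is to classify events by the three attributes the protocol uses (site, causality, seriousness) and see which section 13.5 output each class enters.

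Inputs:

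- Output A, first sentence of section 13.5: ocular events, with no limit on causality or seriousness.
- Output B, second sentence of section 13.5: treatment-related events, with no limit on site or seriousness.
- Collected: all classes (sections 13.1 and 13.3).

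| Site | Causality | Serious? | Output A | Output B | In any planned output? |
|---|---|---|---|---|---|
| Ocular | Related | No | Yes | Yes | Yes |
| Ocular | Related | Yes | Yes | Yes | Yes |
| Ocular | Not related | No | Yes | No | Yes |
| Ocular | Not related | Yes | Yes | No | Yes |
| Non-ocular | Related | No | No | Yes | Yes |
| Non-ocular | Related | Yes | No | Yes | Yes |
| Non-ocular | Not related | No | No | No | **No** |
| Non-ocular | Not related | Yes | No | No | **No** |

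There are 2 × 2 × 2 = 8 classes. Six enter at least one output and two enter none. Those two are the non-ocular events judged not related, nonserious and serious.

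Next, does any other text supply the missing output?

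- Section 10.1 defines who is evaluated for safety, not what is displayed.
- Sections 10.2 and 10.3 name no adverse event table or listing.
- The reporting rules in section 13.3 send serious events to the Medical Monitor and the IRB/IEC, and nonserious forms to the Medical Monitor at study close. This is notification and oversight, not a study output.
- Table 15.1 schedules adverse event monitoring by visit and specifies no analysis.

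None of these fills the two empty classes.

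Last, the edge of Output B is itself unclear. Section 13.3 asks for each event's relationship to the study treatment. The causality section (numbered 12.3.1, within section 13) asks for Related or Not Related to the medical device. Section 13.5 says treatment-related without choosing. Section 9.3.2 puts every subject through surgery and onto postoperative drops. A non-ocular event attributed to the surgery or a drop, but not to the lens, enters Output B on one reading and neither output on the other.

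**The case against.** The strongest reply is that these events are not lost. They are recorded; serious ones reach the Medical Monitor promptly and go to the IRB/IEC; nonserious forms reach the Medical Monitor at study close. That is correct. A reader might infer that the events are collected and then go unreported, or that safety oversight is missing. The documents do not support either inference. The gap is confined to the planned tables and listings.

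A reader might also infer that every non-ocular event is left out. That does not hold, because the treatment-related summary has no ocular limit.

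It is tempting to argue that unmasked causality judgement makes the safety result biased. This adds little. With a single arm there is no between-arm safety comparison to distort, the Medical Monitor also assesses causality, and the definition of Related includes possibly related events. It remains true that causality alone decides whether a non-ocular event appears.

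Nor can it be asserted that events caused by the study drops would be dropped from the results. That depends on the undefined meaning of treatment-related.

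Finally, safety is not among the stated objectives or outcomes, an ocular focus is natural in a lens study, and nothing in section 13.5 forbids showing more. These facts limit the consequence. They support giving ocular events more detail, but they do not explain having no output for serious events that the protocol requires the site to record.

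**Conclusion.** The point holds as a gap in the planned safety outputs. Non-ocular events judged not related, serious and nonserious, are collected but enter neither output in section 13.5, and no other section supplies one. That is two of the eight classes above.

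The effect on this trial's results cannot be sized, because the documents give no expected rate of non-ocular events. For scale only, one such event among the 32 planned subjects would be 1/32 = 3.1% of subjects. That shows what one event means at this sample size; it is not a predicted rate.

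The conclusion assumes that section 13.5 is followed as written and that its second sentence covers events at any site. The primary outcome and the other efficacy results are unaffected. The change is worth making because the omission can include serious events and the correction uses data already held.

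**What to change.** Amend section 13.5 to:

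- tabulate all adverse events, ocular and non-ocular, in all enrolled subjects, matching section 10.1;
- add a listing of every serious adverse event, regardless of site or causality;
- keep the treatment-related summary as a subset of the full table;
- state whether treatment-related means related to the device, as in the causality section, or to the study treatment, as in section 13.3.

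The cost is a few sentences of text, a slightly longer table and one listing. The adverse event forms already hold the information, so no new data collection is needed.

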**14. GCP, ICH and ETHICAL CONSIDERATIONS**

This study will be conducted in compliance with Good Clinical Practices (GCPs), including International Harmonization (ICH) Guidelines, and in general, consistent with the 1996 version of the Declaration of Helsinki. In addition, all applicable local, state and federal requirements will be adhered to.

This study is to be conducted in accordance with Institutional Review Board regulations. The investigator will obtain appropriate IRB/ethics committee approval prior to initiating the study.

The study will be registered with [clinicaltrials.gov](https://clinicaltrials.gov).

## 15. STANDARD EVALUATION PROCEDURES

**Table 15.1. Proposed Visits and Study Assessments**

(visits are by patient, with both eyes tested)

Activity	Pre-operative	Operative	Postoperative			
	Visit 1	Visit 2, 2A	Visit 3, 3A	Visit 4, 4A	Visit 5	Visit 6
			1 Day	1 Week	1 Month	3 Month
Informed Consent	X					
Demographics	X					
General Information: Medical History	X					
Surgery		X				
Manifest Refraction	X				X	X
Uncorrected Distance VA (monocular and binocular)			X	X	X	X
Corrected Distance VA (monocular and binocular)	X				X	X
Uncorrected Intermediate and Near VA (monocular and binocular)					X	X
Distance-corrected Intermediate and Near VA (monocular and binocular)					X	X
Intraocular pressure			X	X	X	X
Verion photograph	X	X			X	X
Quality of vision questionnaire						X
Binocular Defocus curve (uncorrected and corrected)						X
Monitor for Adverse Events		X	X	X	X	X
Complete Exit Form 						X

 Complete Exit Form upon termination of subject participation, or at Visit 6, whichever occurs first.

## 16. CONFIDENTIALITY

No protected health information (PHI), including the patient's name and date of birth, will be collected; to ensure this, no PHI information is permitted to be entered on any of the Case Report Forms (CRFs). Subjects will only be identified by subject IDs and identities will be removed at the initial visit so that there is no further need to protect or destroy the information. Collected information will only be used for purposes of this study and no information will be sold to third parties. The non-PHI information collected may be used for future research, though there is currently no plan to do so.

## **17. FINANCIAL AND INSURANCE INFORMATION/STUDY RELATED INJURIES**

Every effort to prevent study-related injury will be taken by the Study Doctor and staff. In the event a patient is injured as a direct result of the study while following the Study Doctor's instructions and the study requirements, the patient will be instructed to contact his or her doctor immediately. The Study Doctor is to treat the injured subject as needed for those injuries caused directly by this research study. In the event of injury or illness caused by or occurring during a subject's participation in this research study, all charges for medical care provided to the subject will be billed to his or her insurance company. The Study Doctor or Sponsor does not offer to cover the medical care costs for injuries or illnesses that are not caused directly by the research study. The Sponsor does not offer to provide any other compensation, unless specifically agreed to elsewhere in this document. This information will be provided to each study subject before the start of the study in the consent form.

## **18. STUDY ENDPOINT CRITERIA**

### ***18.1. Patient Completion of Study***

If a study patient has completed the final visit (Visit 6) of the study, he/she is considered to have completed the study.

### ***18.2. Patient Discontinuation***

Each study patient may voluntarily discontinue the study at any time they choose. Study patients who cannot complete the study for administrative reasons (e.g., non-compliance, failure to meet visit schedule, etc.) will be discontinued from the study. Study patients discontinued during the enrollment phase (prior to surgery) of the study will be replaced.

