**Table 9.3-1. Visit Schedule**

Visit Number	Visit Name	Visit Window	CRF Number
1	Preoperative	-30 to 0 days from surgery	1
2, 2A	Operative (unilateral)	0 from surgery	2, 2A
3, 3A	1 Day Postoperative	1-2 days postoperative	3, 3A
4, 4A	1 Week Postoperative	7 ( $\pm 2$ ) days postoperative	4, 4A
5	1 Month Postoperative	30 ( $\pm 7$ ) days postoperative	5
6	3 Months Postoperative	90 ( $\pm 15$ ) days postoperative	6

All data collection will be completed through provided Case Report Forms (CRFs). All site personnel involved in the study will be trained in regard to conducting study-specific procedures. Case report forms will be identified by the subject number assigned at the time of randomization. No protected health information (PHI) will be included on any CRF. Subject identities will be removed at the initial visit so that there will be no further need to protect or destroy the information.

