#### 9.3.8. Exit Procedures

In the event of premature exit from the study, all study related examinations should be completed where possible. The Exit CRF should be completed, noting that the subject did not complete the study and the reason for premature study exit. If no premature exit from the study occurs, the Exit CRF should be completed at the end of Visit 6 (Postoperative 3 Months).

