## **11. SAMPLE SIZE JUSTIFICATION**

Data in the literature suggests that the ReSTOR non-toric IOLs (+3.0D and +2.5D) implanted in a group of eligible eyes showed a residual refractive cylinder of  $0.40D \pm 0.32D$ . (Gundersen KG, Potvin R. Comparison of visual outcomes and subjective visual quality after bilateral implantation of a diffractive trifocal intraocular lens and blended implantation of apodized diffractive bifocal intraocular lenses. Clin Ophthalmol. 2016 May 10;10:805-11). We are looking for the toric IOLs to be non-inferior. We powered the study using that mean and SD, a power of 0.9, an alpha of 0.05, and a 0.25D non-inferiority margin. The mean residual refractive cylinders will be compared using a t-test between the two groups, with the mean and SD from the literature (blended bifocal group) and the mean and SD from the current study. The required sample size is 29 subjects. Allowing for 10% dropout we will plan to enroll 32 subjects.

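### Section 18.2 makes discontinuation mandatory for failing the visit schedule, with no threshold, and so can prevent 3-month data being collected that could still be obtained

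*Combined protocol and SAP*

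**What the plan says.** The full sentence in section 18.2 (Patient Discontinuation) is: "Study patients who cannot complete the study for administrative reasons (e.g., non-compliance, failure to meet visit schedule, etc.) will be discontinued from the study". The part at issue here is "failure to meet visit schedule, etc.) will be discontinued from the study". The next sentence gives the only replacement rule in that section: "Study patients discontinued during the enrollment phase (prior to surgery) of the study will be replaced". Section 18.2 sets no number of missed visits and no number of days late.

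Section 9.6 describes discontinued subjects as those without an exit visit, or those exited before the planned last visit. Section 9.3.8 adds: "In the event of premature exit from the study, all study related examinations should be completed where possible". Section 18.1 counts anyone who has completed Visit 6 as having completed the study and attaches no window to that.

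Table 9.3-1 sets the postoperative windows: 1-2 days and 7 ± 2 days after surgery (Visits 3/3A and 4/4A, one of each per eye), 30 ± 7 days (Visit 5) and 90 ± 15 days (Visit 6). Visits 5 and 6 have no separate visit for the second eye, and Table 15.1 states that "visits are by patient, with both eyes tested". Section 9.3 gives each eye its own operative visit.

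Section 11 requires 29 subjects and then says: "Allowing for 10% dropout we will plan to enroll 32 subjects". Section 10 has no rule for missing or out-of-window data.

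**The concern.** The implant is a one-time procedure. A subject who comes late to the 1-week visit still carries both lenses, and their cylinder, acuity and lens orientation can be measured at 3 months as well as anyone else's. A mandatory rule that ends participation for a schedule failure therefore gives up information for no scientific return.

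Two things are at stake. The first is precision: the study is small and its reserve is 3 subjects for all causes together. The second is selective loss. People who miss visits may differ in satisfaction or outcome from those who attend, and section 10 does not say how missing values would be handled. The documents give no direction or size for such a bias, so it is a risk and not a demonstrated effect.

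**Working it through.** **1. The plan's own sample size.** Inputs from section 11: SD 0.32 D, margin 0.25 D, power 0.90, alpha 0.05. Assumptions: true difference zero, and a literature group as large as the study group (its size is not given).

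n = 2 × [SD × (z_alpha + z_power) / margin]² = 2 × [0.32 × (1.645 + 1.282) / 0.25]² = 28.06, rounded up to 29. This reproduces the stated figure if alpha is one-sided 0.05. For dropout, 29 × 1.10 = 31.9, which gives 32 (29 / 0.90 = 32.2 would give 33).

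**2. The reserve.** 32 − 29 = 3 subjects, or 3/32 = 9.4%. Losses after surgery from any cause draw on these 3.

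**3. What discontinuation removes.** By the description in 9.6, a subject discontinued after an earlier miss leaves before Visit 6. Table 15.1 schedules the assessments as follows:

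| Assessment | 1 month | 3 months |
|---|---|---|
| Manifest refraction (source of cylinder) | yes | yes |
| Intermediate and near acuity | yes | yes |
| Verion photograph (orientation) | yes | yes |
| Defocus curve | no | yes |
| Quality of vision questionnaire | no | yes |

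An exit examination under 9.3.8 at, say, week 2 or week 5 is not a 3-month measurement. The defocus curve and questionnaire have no earlier scheduled value.

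**4. Visit 5 with two surgery dates.** Let the second eye be operated on d days after the first. Counting from the first surgery, eye 1 is in window on days 23 to 37 (30 ± 7) and eye 2 on days d + 23 to d + 37. They overlap only if d + 23 ≤ 37, that is d ≤ 14. For Visit 6 the windows are days 75 to 105 and d + 75 to d + 105, which overlap only if d ≤ 30. The documents give no interval between surgeries and do not say which eye's date anchors the shared visits. With d above 14, a fully cooperative subject cannot have both eyes in window at Visit 5.

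**5. Illustration of possible losses.** The documents give no rate of missed windows, so the rates below are assumptions. The table also assumes independence across the six postoperative visits and that every miss leads to discontinuation, which is the strictest reading of 18.2. The probability for a subject is 1 − (1 − p)⁶.

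| p per visit | Subjects discontinued | Expected of 32 | Chance of more than 3 |
|---|---|---|---|
| 1% | 5.9% | 1.9 | 0.11 |
| 2% | 11.4% | 3.7 | 0.50 |
| 5% | 26.5% | 8.5 | 0.98 |

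**6. Effect on power.** Noncentral t, equal groups, other inputs as in step 1.

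| Evaluable subjects | One-sided 0.05 | One-sided 0.025 |
|---|---|---|
| 32 | 0.926 | 0.868 |
| 29 | 0.902 | 0.832 |
| 24 | 0.846 | 0.755 |

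The second power column is shown because section 10.2 makes all tests two-sided at 5%. Losing 8 of 32 subjects costs about 0.08 of power in the first column and 0.11 in the second.

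**The case against.** The strongest reply is that 18.2 governs patients who cannot complete the study, and that a failed schedule is only an example of why. On that reading, a subject with one late visit who then attends Visit 6 has completed the study under 18.1 and does not fit the description in 9.6. Section 9.3.8 also asks for examinations at early exit.

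Much of this stands. A reader might infer that one minor window miss triggers removal, or that data already collected are thrown away. The documents say neither. The efficacy set in 10.1 has no exclusion for late visits; its reference to arcuate incisions is a separate problem. No time point is named for the primary variable, and refraction is also taken at 1 month, so a subject lost after Visit 5 still has a cylinder value. Four of the six visits counted in the illustration (3, 3A, 4, 4A) schedule no manifest refraction.

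A reader might also infer that the rule is incompatible with the 10% allowance. That is not supported either: section 11 limits the allowance to no particular cause, administrative losses are what such allowances normally cover, and no miss rate is given.

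The reply does not dispose of the point. If 18.2 covers only people who cannot attend Visit 6, it is nearly empty. Its verb is mandatory, its examples include non-compliance and the visit schedule, and it sets no threshold. A site could reasonably apply it to an earlier miss, and 9.3.8 would not then supply 3-month data.

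**Conclusion.** The point holds as a weakness in a stated rule that is cheap to improve. Section 18.2 permits, and on a plain reading may require, ending participation before Visit 6 for schedule failures that do not stop the 3-month outcomes being measured. The reserve is 3 subjects, and no replacement is stated after surgery.

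The size of the loss cannot be derived from the documents. The figures of 3.7 and 8.5 subjects rest wholly on assumed per-visit rates of 2% and 5% and on the strictest reading. Even with 24 evaluable subjects, power is about 0.85 at the one-sided 0.05 that reproduces 29, given a literature group of equal size. The more durable reason to act is avoidable and possibly selective loss of 3-month data with no rule for handling it.

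The 14-day result for Visit 5 is exact, but it affects a subject only if the surgeries are further apart than that, which the documents leave open.

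**What to change.** In 18.2, record a missed or late visit as a protocol deviation. The subject stays in the study and is examined at Visit 6 whatever was missed earlier, unless they withdraw or are lost to follow-up. The safety provisions in 9.6 and 18.3 are not touched by this change.

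Record the actual days since surgery for each eye at Visits 5 and 6, and state in Table 9.3-1 how the windows apply when the two surgery dates differ.

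In section 10, include the late data in the primary analysis and add one sensitivity analysis limited to in-window visits.

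The cost is a sentence or two in 18.2, a note to the visit table, one recorded value per eye per shared visit, and one extra analysis. The downside is that a few out-of-window measurements enter the primary analysis; the sensitivity analysis shows whether they matter.
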